Using an uSmart NexGen Ultrasound 3300 (Terason, Burlington, MA) equipped with two-dimensional imaging, color and spectral Doppler, an internal electrocardiogram (EKG) monitor and a

[figure not shown]

Figure 3: Example of flow-mediated dilatation in a healthy volunteer from 24 Aug 2017

duplicate. The change in post-stimulus diameter at peak dilation as a percentage of the baseline diameter will be reported as endothelial function.

Analysis will be automated using a validated software (Vascular Analysis Tools 6, MIA-LLC, Coralville, IA). We have reported a clinical trial using FMD from our laboratory ¹⁸. **Figure 3** shows the results of FMD from our laboratory in a normal healthy volunteer using the above software. Although FMD requires an ultrasound machine, high frequency transducers, and a trained technician capable of measuring the diameter of the brachial artery before and after ischemia in a reproducible manner, we use the FMD technique because it is the reference standard for endothelial function ^{94,95}. We have previously reported FMD to be 12.9% in normal healthy volunteers with within-subject standard

high frequency vascular transducer (16 to 5 mHz, 16L5 probe), ultrasonography will be performed by a trained technician using a standardized protocol ^{91,92}.

Participants will be positioned supine with the arm placed in a comfortable position to image the brachial artery in a longitudinal plane. A segment of brachial artery 5-10 cm above the elbow with clear anterior and posterior intimal interfaces between the lumen and the vessel wall will be selected. A sphygmomanometric cuff placed on the forearm will be rapidly inflated to suprasystolic pressure (250 mmHg) for 5 minutes to produce ischemia using an air source coupled to a rapid cuff inflator (Hokanson E 20 Rapid Cuff Inflator; E.C. Hokanson, Inc).

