Longitudinal resting images will be acquired before inflation. Blood flow estimated by the pulsed Doppler velocity signal using the outer envelope technique to calculate the velocity time integral will be obtained from a mid-artery sample volume at baseline and upon immediate cuff release to assess hyperemic velocity. Peak hyperemic velocity will be determined from the first complete velocity envelope after cuff release. Higher values of hyperemic velocity represent better microvascular dilatation ⁹³. Longitudinal images of the artery in B mode will be continuously recorded for 3 min after cuff deflation. Images will be recorded digitally using an R-wave gated digitizing interface external to the machine (MIA- LLC, Coralville, IA).

A few minutes after deflation, another image will be acquired to reflect a reestablished baseline. The above procedure is repeated to acquire the images in

deviation of 0.93% and between-subject standard deviation of 1.77%. Thus, the test-retest coefficient of variation was 7.2% in our laboratory.

Biomarker measurements

We may use specimen collected as part of this study for analysis of DNA which may include whole genome sequencing. Plasma endothelin-1 will be measured using validated ELISA kits (R&D systems, Inc., Minneapolis, MN). 24h urinary nitrite and nitrate and total nitrates will be measured using the Greiss reaction using kits from R&D systems, Inc. Renin and aldosterone will be measured using a commercial laboratory (LabCorp, Burlington, NC). Plasma ADMA will be measured using LCMS in our biochemistry core lab. The usual labs such as blood counts, chemistries, urine albumin and Na will be measured in the hospital laboratory. Renin + aldosterone lab testing will require the participants to be resting in seated position for at least 15 minutes prior to blood draw.

STATISTICAL METHODS

Outcome Variables

The outcome variables are as follows:

1. Change from baseline to 12 weeks in diastolic BP in EPO treated patients compared to delayed start controls. In the waitlisted group, we will measure the change from 12 weeks to 24 weeks compared to the change from 0 to 12 weeks.

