2. Change from baseline to 12 weeks in systolic BP in the comparisons above. Between group change in hypertension status from baseline to 12 weeks. Worsening of hypertension at any time point will be defined either as an increase in BP medication or an increase in seated clinic diastolic BP of ≥ 10 mmHg or systolic BP ≥ 20 mmHg. Within-group change in hypertension status from 12w to 24 w will be compared to the control period of 0 to 12w in the delayed start group.
3. The primary outcome variable in this aim is to examine the change in FMD from baseline to 4 weeks in those treated with EPO compared to the waitlisted group. The hypothesis being tested is that EPO will cause impairment in endothelial function. Accordingly, those on EPO will have worsening of FMD.
4. The primary outcome variable in this aim is to examine the predictors of change in FMD from baseline to 4 w in those treated with EPO compared to time controls. Predictors of this change will be baseline values of the following variables: ADMA, urine nitrate and nitrite, renin, aldosterone, and plasma endothelin-1 and change from baseline to 4 w in the above variables. This analysis will answer the question: which of the pathways independently is predictive of endothelial dysfunction?

Sample Size

The primary objective of the study is to assess the change from baseline to 12 weeks in diastolic BP in EPO treated patients compared to controls. In the waitlisted group, we will measure the change from 12 weeks to 24 weeks compared to the change from 0 to 12 weeks. We have measured 24h

ambulatory BP in 183 CKD patients 4 weeks apart. The mean diastolic BP at baseline was 68.3 mmHg and at 4 weeks 68.1 mmHg. The mean difference was 0.14 mmHg and the standard deviation of the difference was 10.3 mmHg. With these assumptions, two-tailed tests and 80% power, the required sample size to detect a between-group difference of 5 mmHg is 68 subjects completing the study in each group. Assuming 85% of those randomized complete the trial, we would need to randomize $68/0.85 = 80$ subjects per group, or 160 subjects in total.

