The standard deviation of the difference in systolic BP is 16.7 mmHg and we can detect an 8.4 mmHg between-group difference using the above assumption. The assessment of endothelial function is another major goal of this application. Position papers on FMD studies 90 state the following: "Typically, significant improvement in FMD can be seen with 20 to 30 patients in a crossover design study and 40 to 60 patients in a parallel-group design study. In studies of this size, the minimal statistically significant improvement that can be detected with intervention is an absolute change in FMD of 1.5% to 2%." The SD of absolute change within subjects in our lab is 0.93%. The sample size proposed (160) will allow us to detect a change of as little as 0.45%. Notably, this change is much more sensitive—approximately one quarter of what is commonly seen with typical sample sizes in conventional FMD studies.

Analysis

The analyses will begin with descriptive statistics. Overall and by-group descriptive statistics will be calculated and examined graphically. Tests for differences in demographics between the early and delayed start groups and characteristics of dropouts will be computed using t-tests, chi square (or Fisher's exact tests if $n < 6$ per cell) to understand if potential differences exist, although such differences are not expected. Comparison of the three UACR strata will be done to assess if there are differences in the populations recruited. Randomization will be within UACR group so that these differences should not bias the trial.

Primary Analysis

To test the hypothesis that early start EPO will worsen the 24-hour DBP assessed by change from baseline to 12 weeks, a mixed model will be used to analyze the results.

We will fit two separate models:

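### The 0.93% behind the 0.45% detectable FMD difference is called a within-subject SD in one section and an SD of change in another; if it is the former, the figure is about 0.64%

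*Combined protocol and SAP*

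**What the plan says.** The Sample Size section gives the input as "The SD of absolute change within subjects in our lab is 0.93" percent and concludes: "The sample size proposed (160) will allow us to detect a change of as little as 0.45" percent. It compares this with the 1.5% to 2% absolute change that it quotes from a position paper, calling it roughly "one quarter of what is commonly seen with typical sample sizes in conventional FMD studies". The Objectives section repeats 0.45% in support of a statement that power is adequate.

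The same number appears under Measurement of endothelial dysfunction, in a sentence that the page layout splits in two: "We have previously reported FMD to be 12.9% in normal healthy volunteers with within-subject standard" and then "deviation of 0.93% and between-subject standard deviation of 1.77%. Thus, the test-retest coefficient of variation was 7.2% in our laboratory".

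That section also says of the scan "The above procedure is repeated to acquire the images in" duplicate, and defines the endpoint thus: "The change in post-stimulus diameter at peak dilation as a percentage of the baseline diameter will be reported as endothelial function". It does not say whether the two acquisitions are averaged. The clinic BP section, by contrast, states that three readings are averaged.

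For diastolic BP the plan uses an SD of the difference, 10.3 mmHg, from 183 CKD patients measured 4 weeks apart. It assumes 80% power with a two-sided comparison and states that "the required sample size to detect a between-group difference of 5 mmHg is 68 subjects completing the study in each group". No retest interval or number of subjects is given for the FMD figure.

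**The concern.** A within-subject SD describes the scatter of one FMD value around a person's own mean. An SD of change describes the scatter of a difference between two such values. With independent errors of equal size at two visits, the second is the first multiplied by the square root of 2. One number cannot normally be both.

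The CV indicates how the methods section treats 0.93%: dividing it directly by the mean FMD of 12.9% gives 7.2%, which is the CV based on a within-subject SD. The power statement treats 0.93% as an SD of change.

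FMD change from baseline to 4 weeks is the primary outcome of its own aim and the proposed mediator of the BP effect. The 0.45% figure is the plan's only numerical statement of sensitivity for that outcome. As written, a reader cannot tell whether power at 0.45% is 80% or nearer 50%.

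**Working it through.** **Inputs.** SD 0.93%, mean FMD 12.9%, and duplicate acquisition (Measurement of endothelial dysfunction; Sample Size). Two-tailed tests, 80% power, 68 completers per group from 80 randomized, and diastolic SD of difference 10.3 mmHg (Sample Size). Alpha is not stated in the documents; 0.05 is assumed.

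**Formula.** For a comparison of mean change between two equal groups, the detectable difference is SD of change × √(2/n) × (1.960 + 0.842). The t-based version is slightly larger and is used for the conclusions.

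**Check of alpha on the plan's diastolic figure.** 10.3 × √(2/68) × 2.802 = 4.95 mmHg; t-based 4.98. The plan says 5, so alpha 0.05 fits.

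**Reproduction of the FMD figure.** 0.93 × √(2/68) × 2.802 = 0.447%; t-based 0.450%. The plan's 0.45% is therefore correct for an SD of change of 0.93% and 68 per group.

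**What each label implies for the other section.**
- Within-subject SD of 0.93% at each visit: SD of change = √2 × 0.93 = 1.32%.
- SD of change of 0.93%: within-subject SD = 0.93/√2 = 0.66%, and CV = 0.66/12.9 = 5.1%, not 7.2%.
- Single-scan SD of 0.93%, two scans averaged at each visit, no visit-to-visit variance: per-visit variance = 0.93²/2, so SD of change = √(2 × 0.93²/2) = 0.93%. Only on this set of conditions do both sections stand as written.

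**Detectable difference and power (t-based, two-sided 0.05, 80% power).**

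| Meaning of 0.93% | SD of change | Detectable, 68 per group | Detectable, 80 per group | Power at 0.45%, 68 / 80 |
|---|---|---|---|---|
| SD of change | 0.93% | 0.450% | 0.414% | 80% / 86% |
| Per-visit within-subject SD | 1.32% | 0.636% | 0.586% | 51% / 58% |

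Both group sizes are shown because FMD change is measured at week 4, when the number available may lie between 68 and 80.

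**Comparison with the quoted 1.5% to 2%.** 0.45/2 = 22.5% and 0.45/1.5 = 30%, which is about a quarter. 0.636/2 = 32% and 0.636/1.5 = 42%, which is about one third to two fifths.

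**Effects the plan regards as usual.** The Hypothesis section says most FMD studies are powered for changes of 1% to 2%. With SD of change 1.32%, power for a 1% difference is 99.3% with 68 per group and 99.8% with 80; it is higher for larger effects.

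**The case against.** The strongest reply is that the Sample Size section states its input outright as an SD of change. With the test, power and completers given there for diastolic BP, 0.45% follows. The source that would settle the meaning of 0.93% is an earlier report that is not part of these documents, so the error may lie in the methods label and the CV, with 0.45% sound. This stands: the documents show a conflict, not which side is wrong. A reader might infer that 0.45% is an arithmetic mistake; the documents do not support that.

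Averaging the duplicates could also reconcile the two labels. It could, but only with negligible visit-to-visit variance, and the plan states neither condition.

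A reader might further infer that the FMD aim is underpowered. It is not shown to be. The 0.45% is a claimed sensitivity, not a hypothesized effect, diastolic BP determines the sample size, and power for effects of 1% to 2% is about 99% or more on either reading.

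Nor is it an error that the plan attaches 0.45% to 160 participants although the figure corresponds to 136 completers. The same section derives 160 from 68/0.85 per group, so 160 reasonably names the design with its dropout allowance. If all 160 were analysed, 0.45% would have 86% power.

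**Conclusion.** The conflict between the two sections is real, and unless the unstated averaging conditions hold, at least one stated figure needs correcting: the 0.45% and its comparison with other studies, or the within-subject label and the 7.2% CV. The methods section supports the per-visit reading, on which the detectable difference is about 0.64% (0.59% with 80 per group) and power at 0.45% is about 51% (58%). That reading is not proven.

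These figures assume two-sided alpha 0.05, independent errors of equal variance at the two visits, an unadjusted comparison of change, and that an SD from healthy volunteers carries over to anemic CKD patients. The last point cannot be checked from the documents and applies to the plan's 0.45% as well. The design is not threatened and the sample size needs no change; a stated sensitivity claim may simply not be delivered.

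**What to change.** Check the source of 0.93%, then do one of the following.

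- **Per-visit within-subject SD:** replace 0.93% in the Sample Size section by the SD of change (about 1.32%). Restate 0.45% as about 0.64% with 68 per group, there and in the Objectives section. Change the comparison from about one quarter to about one third to two fifths of 1.5% to 2%.
- **SD of change between visits:** keep 0.45%, and correct the label and the CV under Measurement of endothelial dysfunction (0.66% and 5.1%).
- **Single-scan SD with duplicates averaged in the trial:** say so in the measurement section, and compute the SD of change on that basis, allowing for visit-to-visit variance.

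In every case, state that the FMD figure uses 68 completers per group, give the alpha, and say that the SD comes from healthy volunteers and not from CKD patients.

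The cost is a few sentences and possibly a less favourable stated sensitivity. No additional participants and no change to study procedures are needed.

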Harms will be assessed by monitoring changes in weight, eGFR, CBC, clinic BP, and ABPM. For more definitive assessments, including hospitalizations, serious adverse events will be properly completed and sent to the VAMC DMC as requested. Safety of continued participation will be assessed at each study visit. The stop-points will be treatment-emergent severe adverse events that precludes further exposure to the drug, such as an allergic drug reaction, initiation of renal replacement therapy, or death. If the study drug is stopped, the subject will be continued to be studied so as to not violate the intention-to-treat principle.

Participants

Inclusion Criteria

- Stage 3 or 4 CKD defined as eGFR <60mL/min/1.73m² for ≥3 months or persistent albuminuria for ≥3 months; (i) urine albumin to creatinine ratio of more than 30 mg/g; (ii) urine protein to creatinine ratio of more than 150 mg/g; or (iii) at least 1+ dipstick positive proteinuria. ⁸⁸
- 24h ABPM <140/90 mmHg at baseline in the presence or absence of antihypertensive treatment.
- Hgb between 8 and 10 g/dL.
- No treatment with ESA within the previous 3 months.
- Adults, age 18 and older.

Exclusion Criteria

- Need for packed RBC transfusion in the previous 2 months.
- Myocardial infarction, stroke, or hospitalization for heart failure in the past 2 months.
- In the assessment of the investigator, have hematologic, inflammatory, infectious, or other conditions that might interfere with the erythropoietic response.

Retention of Participants

For half of the participants, only 7 visits are needed. For the others, at least 11 visits over 24 weeks of the trial are needed. We will offer \$20 per visit for participation in the trial to offset travel and time costs.

METHODS

Method of Randomization

Participants will be randomized in a 1:1 ratio to either early or delayed treatment (“waitlisted group”) with EPO according to UACR strata. A random permuted block design will be used to avoid imbalance in assignment to the treatment groups over time. A randomization sequence will be generated by the statistician and individually concealed in sequentially numbered opaque envelopes. After confirming eligibility with the principal investigator, the study pharmacist will dispense EPO according to the randomization sequence.

Measurement of clinic BP

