- model 1: The outcome variable will be 24h ambulatory diastolic BP. The predictors will be indicator variables for group (early or late start), time (baseline and 12 weeks), stratum (UACR: none, high, very high) and all interactions. The random component of the mixed model will include subject and time. Unstructured covariance will be used with estimation of marginal means by maximum likelihood. We expect the interaction between group by time to be significant. The random coefficient analysis does not require baseline systolic BP as a covariate. If the 3-way interaction term (group x time x stratum) is significant, then results will be reported within each stratum. Confirmatory analyses will utilize change from baseline in clinic diastolic BP.
- model 2: The outcome variable will be 24h ambulatory diastolic BP. The predictors will be indicator variables for period within the delayed start group (early or late), time (baseline and 12 weeks from start of period), stratum (UACR: none, high, very high) and

all their interactions. The random component of the mixed model will include subject and time. We expect the interaction between period by time to be significant. If the 3-way interaction term is significant, then results will be reported within each stratum.

Accounting for missing data

Ambulatory BP recording, the gold-standard to assess BP, is carried out only twice during the trial in the parallel group analysis, but clinic BP measurements occur every 4 weeks. Patients who drop out but have some post-baseline measurements of clinic BP will be included in the analyses, thus minimizing loss to follow up. We will impute ambulatory BP as follows: we will use the complete data to build a model that relates the follow-up mean 24-hour ambulatory diastolic BP from the baseline 24-hour ambulatory diastolic BP and the clinic measures using repeated measures Mixed Model regression - then use the expected value from the model for the missing value - and use PROC MI (which generates maybe 5 replicate values to insert variability into the imputation) so that there is a price to pay for imputing.

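### Model 1 is fitted by maximum likelihood, which makes the standard error of the primary contrast about 2% too small; its covariance wording also permits a redundant specification

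*Combined protocol and SAP*

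**What the plan says.** Model 1 (Statistical Methods, Primary Analysis) takes 24-hour ambulatory diastolic BP as the outcome. Its fixed effects are group, time (baseline and 12 weeks), UACR stratum (three levels) and all their interactions. On the covariance and the estimator it says:

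- "The random component of the mixed model will include subject and time"
- "Unstructured covariance will be used with estimation of marginal means by maximum likelihood"

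The same paragraph calls this a random coefficient analysis. The section Accounting for missing data confirms that the parallel-group comparison has only two ambulatory recordings per patient.

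The plan does not say whether the unstructured matrix is that of the random effects or that of the residuals, or whether a separate residual variance is kept. It names no method for denominator degrees of freedom.

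**The concern.** There are two separate issues.

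**Estimator.** Maximum likelihood divides the residual sums of squares by the number of patients and ignores the means that were fitted. With six means per visit, the variance is biased down. The interval for the primary contrast is then too short and its p-value too small.

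**Covariance wording.** Two readings per patient provide two variances and one covariance. A random intercept and a random time effect with an unstructured matrix use up all three, so a residual variance on top is one parameter too many. Software may then report non-convergence or a Hessian that is not positive definite. The plan has no fallback for that, so the model could be changed ad hoc, after the data are seen, in an open-label trial.

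**Working it through.** **Inputs.** From Sample Size: for the change in 24-hour diastolic BP, "the standard deviation of the difference was 10.3 mmHg". The same section sets a two-sided test at 80% power, a target difference of 5 mmHg, 68 completers per group and 85% completion. From Method of Randomization: 1:1 allocation. From model 1: 2 groups × 3 strata = 6 means per visit, 12 in all. Assumptions: alpha of 0.05 and complete pairs of readings.

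**1. The plan's own figure.** n per group = 2 × (1.960 + 0.842)² × 10.3² / 5² = 66.6, so 67 with the normal formula. The t-based solution is 67.6, so 68. Then 68/0.85 = 80 per group and 160 in total. The stated sample size reproduces, which supports taking alpha as 0.05 two-sided.

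**2. Standard error under ML and REML.** With complete pairs and the same six cells at both visits, ML divides by n and REML by n − 6. The ratio of standard errors is √((n − 6)/n), whatever weights the strata receive.

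- n = 136 (2 × 68): √(130/136) = 0.978
- n = 160: √(154/160) = 0.981

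On the mmHg scale at n = 136, taking the strata as evenly spread, the REML standard error is 10.3 × √(4/136) = 1.766. The ML standard error is 1.766 × 0.978 = 1.727.

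**3. Type I error.** The actual level is P(|t| > critical value × ratio), with t on n − 6 degrees of freedom.

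| n | ML, t reference | ML, normal reference | REML, normal reference |
|---|---|---|---|
| 136 | 5.5% | 5.8% | 5.2% |
| 160 | 5.4% | 5.6% | 5.2% |

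REML with a t reference gives 5.0%. REML with a normal reference already gives 5.2%, so about 0.2 points of the 5.6% to 5.8% belong to the normal reference.

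**4. Interval at n = 136.** The t multiplier on 130 degrees of freedom is 1.978. The 95% half-width is 1.978 × 1.766 = 3.49 mmHg under REML and 1.978 × 1.727 = 3.42 mmHg under ML. ML with a normal multiplier gives 1.960 × 1.727 = 3.38 mmHg.

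**5. Parameter count.** Code time as 0 and 1. Let the random-effects matrix have elements g11, g12, g22 and let the residual variance be s². Then:

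- variance at baseline = g11 + s²
- covariance = g11 + g12
- variance at week 12 = g11 + 2·g12 + g22 + s²

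This is four parameters for three moments, and the mapping has rank 3. Adding 1 to s² and g12 while subtracting 1 from g11 and 2 from g22 changes none of the three moments. Two other readings of the same sentences have three parameters and are identified: one unstructured 2×2 within-patient matrix, and independent subject and time effects with a residual.

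**6. Does the redundancy reach the primary contrast?** I fitted the four-parameter version to one simulated data set of 136 patients. The SD of change was 10.3 mmHg; the SD at each visit was assumed to be 11 mmHg, which the documents do not give. Under ML, five starting values gave residual variances from 1.6 to 18.5. All five gave the same log-likelihood (−740.386), marginal covariance, group-by-time estimate (−2.122) and standard error (1.687). Under REML the estimate was the same and the standard error was 1.725, so the ratio is again 0.978.

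**The case against.** The best case for leaving the text alone has four parts.

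- **ML is a standard, consistent estimator.** At this sample size it adds only about half a percentage point to the type I error, and it shortens the half-width by 0.07 mmHg against a design difference of 5 mmHg. This stands as an argument about size. It does not remove the bias.
- **The covariance sentence need not mean the redundant model.** It can be read as a single within-patient matrix, and the plan refers elsewhere to repeated measures mixed models in PROC MIXED, for clinic BP. This also stands. However, the random coefficient label points the other way, and a primary model should not leave the choice open.
- **The analysed number is not settled.** Patients who drop out but have clinic BP data are to be kept, with their ambulatory BP imputed. The number therefore lies between 136 and 160, and multiple imputation will itself change the final standard error. This stands, and it is why both ends are shown.
- **No reference distribution is specified.** The normal-reference figures are therefore one possibility and should not be charged to ML in full.

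A reader might go further and infer that the primary model cannot be fitted uniquely, or that its test is invalid. The documents do not support that. It requires one particular reading of the sentence. Even on that reading, only the division between random-effect and residual variance is undetermined, and the primary test does not use that division.

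**Conclusion.** The concern holds as a minor point about precision and specification. As written, model 1 understates the standard error of the group-by-time contrast by about 2%. A nominal 5% test runs at about 5.4% to 5.5% with a t reference, or 5.6% to 5.8% if a normal reference is used as well. That would not by itself overturn a clear result.

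The covariance wording is ambiguous, and one natural reading of it is over-parameterised. The practical risk is a convergence or Hessian warning and an unplanned response to it, not a wrong estimate.

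The error rates rest on alpha of 0.05, complete pairs for 136 to 160 patients, and the reference distribution named with each figure. The standard error ratio rests only on complete pairs and six means per visit.

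**What to change.** Replace the two sentences on random effects and estimation in model 1 with wording such as:

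> Model 1 will be fitted by restricted maximum likelihood with one unstructured 2×2 covariance matrix for each patient's baseline and 12-week readings, no additional random effects, and Kenward-Roger degrees of freedom.

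Three covariance parameters then match three moments, the ML bias is removed, and with complete pairs the point estimate is unchanged. Model 2 repeats the subject-and-time phrase without naming a covariance structure or an estimator. It should be clarified in the same edit with its own statement, because delayed-start patients have three ambulatory recordings.

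The cost is SAP wording and an interval about 2% wider, for example a half-width of 3.49 instead of 3.42 mmHg at 136 completers. No new data, patients or visits are needed.

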Clinic BP measurements will be obtained by a trained observer in triplicate in both arms after applying an appropriately sized cuff using a digital oscillometric sphygmomanometer (Model HEM-907, Omron Healthcare) following the recommendation of the European Society of Hypertension ⁸⁹. The arm and the forearm will be supported at the level of the heart (mid-sternum) and oscillometric BP will be measured after 5 min of seated rest without an observer in the room. Measurements averaged over three readings at 1 min intervals will be used to define clinic visit BP. The left arm will be used for all measurements, unless between arm reading exceed 5 mmHg systolic. If so, the arm with the higher BP will be designated the “BP arm” and will be used for clinic BP measurements. If a subject has dialysis access (AV fistula or AV graft), we will use their non-access arm for all BP measurements.

Measure of 24-hour ambulatory BP

Ambulatory BP monitoring will be performed in all participants at baseline prior to randomization and at the end of the treatment period as indicated in **Figure 2**. Appropriately sized cuffs will be used with bladder sizes that encircle 80–100% of arm circumference and widths that are at least 40% of arm circumference. We will measure ABP every 20 minutes from 06:00 – 22:00 and every 30 minutes from 22:00 – 06:00 based upon a prior protocol using the use the Spacelabs 90207 monitor ¹⁷. Participants will be asked to record their wake and sleep times into diaries; the latter are used to calculate diurnal ambulatory BP. At least 16 recordings will be required to call 24h BP adequate (excluding readings taken for monitor validation during ambulatory dispensing). All ambulatory BP measurements will be taken on a subject’s non-dominant arm. If a subject has dialysis access, all BP measurements will be completed on the non-access arm.

Measurement of endothelial dysfunction

We will instruct the participants to fast for eight hours, refrain from caffeine, alcohol and tobacco and avoid exercise for 8 hours prior to testing. Endothelial function testing will be performed using flow-mediated dilatation (FMD) in a quiet, temperature-controlled room with dimmed lights after the participant has been resting for at least 15 minutes in the recumbent position using international recommendations ⁹⁰.

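### Free improvement: adjust the primary 24h diastolic BP comparison for baseline 24h diastolic BP, which Model 1 uses only as an outcome level

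*Combined protocol and SAP*

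**What the plan says.** The Primary Analysis section sets out "To test the hypothesis that early start EPO will worsen the 24-hour DBP assessed by change from baseline to 12 weeks". Model 1 takes 24h ambulatory diastolic BP at both visits as the outcome. Its predictors are "group (early or late start), time (baseline and 12 weeks), stratum (UACR: none, high, very high) and all interactions". On estimation it says: "Unstructured covariance will be used with estimation of marginal means by maximum likelihood". The effect of interest is group by time. On baseline it says: "The random coefficient analysis does not require baseline systolic BP as a covariate". Results are to be reported by stratum if the three-way term is significant.

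Three other places bear on this:
- **Measure of 24-hour ambulatory BP:** "Ambulatory BP monitoring will be performed in all participants at baseline prior to randomization".
- **Inclusion Criteria:** entry requires "24h ABPM <140/90 mmHg at baseline in the presence or absence of antihypertensive treatment".
- **Sample Size:** for 24h diastolic BP measured 4 weeks apart, "The mean difference was 0.14 mmHg and the standard deviation of the difference was 10.3 mmHg". The calculation uses "two-tailed tests and 80% power" and arrives at 68 completers per group for a 5 mmHg difference.

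**The concern.** Model 1 includes the baseline reading, but only as an outcome level whose mean may differ between arms. Randomization makes the true baseline means equal, so leaving them free discards information. The group by time effect then subtracts the whole baseline value from each patient's week-12 value, whether or not a slope of one is the best use of it. Regressing week 12 on baseline, or constraining the arms to share one baseline mean, lets the data choose the slope.

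It is correct that the model does not need a baseline covariate to be valid, but that is not a reason to give up precision. The measurement is already in hand, and elsewhere the plan uses baseline values in just this way: baseline 24h diastolic BP enters the imputation model, and baseline FMD is a covariate in the FMD regression.

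A related gap is that all stratum interactions stay in the primary model, so group by time is not one number until the stratum weights are fixed. The reference to marginal means suggests averaging over strata, but does not say whether the weights are equal or proportional to stratum size.

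At stake is precision in a trial sized with almost no slack: 67 rather than 68 completers per group gives 79.7% power.

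**Working it through.** **Inputs from the documents.** Difference 5 mmHg; SD of change 10.3 mmHg; 68 completers per group; two-tailed; 80% power; three UACR strata.

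**Assumed, because the documents do not give them.** Alpha 0.05; correlation ρ between baseline and week-12 24h diastolic BP, 0.5 to 0.8; ratio k of baseline SD to week-12 SD, 1.0, 0.9 or 0.8; stratum shares.

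**1. The plan's own figure.** The standard error is 10.3 × √(2/68) = 1.77 mmHg. The noncentral t calculation gives 80.2% power, and 68 is the smallest n per group that reaches 80%. The detectable difference at 80% power is 4.98 mmHg. Then 68/0.85 = 80 per group. The sizing reproduces as a two-group comparison of change scores.

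**2. What Model 1 tests.** In simulated complete data with all group, time and stratum interactions, each difference between the week-12 and baseline coefficients equalled the matching coefficient from a regression of change on group, stratum and their interaction (largest gap 2 × 10⁻¹⁴). The group by time effect is therefore a difference in mean change, averaged over strata by whatever weights are chosen.

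**3. Power after baseline adjustment.** Hold the SD of change at 10.3:
- week-12 SD = 10.3 / √(1 + k² − 2ρk)
- residual SD = week-12 SD × √(1 − ρ²)

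Example, k = 1 and ρ = 0.6: week-12 SD = 10.3/√0.8 = 11.52; residual SD = 11.52 × √0.64 = 9.21; variance ratio (9.21/10.3)² = 0.80; power 88.1%.

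Each cell gives the variance ratio to the change score, then power at 68 per group:

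| ρ | k = 1.0 | k = 0.9 | k = 0.8 |
|---|---|---|---|
| 0.5 | 0.75, 90.1% | 0.82, 87.2% | 0.89, 84.5% |
| 0.6 | 0.80, 88.1% | 0.88, 85.1% | 0.94, 82.5% |
| 0.7 | 0.85, 86.2% | 0.93, 83.1% | 0.98, 81.0% |
| 0.8 | 0.90, 84.2% | 0.97, 81.3% | 1.00, 80.2% |

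The detectable difference falls from 5.0 mmHg to 4.3–4.7 (k = 1.0), 4.5–4.9 (k = 0.9) or 4.7–5.0 (k = 0.8). Chance baseline imbalance lowers each power by about 0.3 points. The smaller values of k are shown because the ABPM entry limit may narrow the baseline spread.

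**4. Stratum weights.** With equal weights on three strata of share p, the variance of the overall change contrast is multiplied by (1/9) × Σ(1/p):
- equal shares: 1.000, power 80.2%
- 40/35/25: (2.5 + 2.857 + 4)/9 = 1.040, power 78.7%
- 50/30/20: (2 + 3.333 + 5)/9 = 1.148, power 74.6%

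If effects differ by stratum, the weights also change what is estimated. With assumed effects of 3, 5 and 8 mmHg and shares 50/30/20, equal weights target (3 + 5 + 8)/3 = 5.3 mmHg, and proportional weights 0.5×3 + 0.3×5 + 0.2×8 = 4.6 mmHg.

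**5. Simulation of the proposed test.** With 4,000 trials per setting, a uniform 5 mmHg effect and 50/30/20 strata, the baseline-adjusted test with stratum main effects had 84–90% power at k = 1.0 and 80–84% at k = 0.8. The equal-weight change contrast had 74–75%.

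**The case against.** The strongest reply is that nothing here is an error. The planned test is valid, uses the endpoint as stated, and agrees with the basis of its sample size. The benefit rests on a correlation and an SD ratio that the documents do not report, and at one corner of the table it is zero. All of that stands, and it is why the point is an improvement and not a fault. It does not defeat the change: in large samples adjustment is not less precise than the change score, and the cost is one degree of freedom. The endpoint is also unaffected, because regressing change on baseline and group gives the same group estimate as regressing the week-12 value on them.

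A second reply is that baseline already contributes for dropouts, through maximum likelihood and the planned imputation. This stands in part. Crediting Model 1 with baselines from all 80 randomized per arm under maximum likelihood (missing at random) puts its power at 80–82%. The gain is then about 3–8 points (k = 1.0), 1–6 (k = 0.9) or 0–4 (k = 0.8). Any further contribution from imputation based on clinic BP was not quantified. Imputation and baseline adjustment can be used together.

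Two stronger readings should be set aside. A reader might infer that the plan refuses adjustment for baseline diastolic BP. The sentence says only that a covariate is not required, and it names systolic pressure, so what the documents show is an absence from the predictor list. A reader might also infer that Model 1 is simply the raw two-group difference in change. It is not, because stratum and all its interactions are in the model.

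**Conclusion.** The point holds as a free gain in precision. Model 1 makes no baseline adjustment in its group by time test, although a pre-randomization value exists for every participant. At 68 completers per group, the 80.2% of the plain change-score comparison would become 84–90%, 81–87% or 80–85% for k of 1.0, 0.9 or 0.8. This assumes ρ of 0.5–0.8, SD of change 10.3 and two-sided alpha 0.05. The true gain could be close to nothing.

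The documents do not support calling the primary analysis biased or the trial undersized. The 79% and 75% figures apply only if the all-interactions model is averaged with equal stratum weights and the strata are split as assumed; with equal strata there is no loss. The unstated weights and the word systolic are clarifications, secondary to the baseline adjustment.

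**What to change.** 1. Make the primary test the between-arm difference in week-12 24h diastolic BP, adjusted for baseline 24h diastolic BP, with UACR stratum as a main effect. Either ANCOVA or the same two-visit mixed model with a common baseline mean across arms will serve.
2. Apply the same model to the observed data and to each imputed data set.
3. Move the group by time by stratum test to a supportive model. Stratum results can still be shown, and the primary contrast no longer depends on unstated weights. If the all-interactions model is kept as primary, state the stratum weights.
4. Reconcile the reference to baseline systolic BP with the diastolic outcome.

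The cost is SAP wording only: no new data, visits or participants, and the sample size can stay as it is.
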